6.2. Secondary Outcome Measures

6.2.1. Comparison of AHI between unattended and in-laboratory polysomnography
6.2.2. Comparison of average SPO₂ between unattended and in-laboratory polysomnography

6.2.3. Comparison of SPO₂ nadir between unattended and in-laboratory polysomnography

6.2.4. Comparison of sleep disordered breathing diagnosis between unattended and in-laboratory polysomnography

6.3. Exploratory Outcomes Measure: Comparison of McGill Oximetry Scores between unattended and in-laboratory polysomnography.

6.4. Analysis: The primary outcome is the feasibility of obtaining an adequate sleep study from unattended polysomnography in pediatric patients. Percentages of studies that have 6 hours of data sufficient for analysis will be reported. The study will be defined feasible if 85% or more of participants provide 6 or more hours of analyzable data. Descriptive statistics will be used to describe the AHI, SPO₂ nadir, SPO₂ average, and diagnosis obtained using each method. Continuous secondary outcome measures will be compared using paired-t tests or its non-parametric equivalent Wilcoxon signed rank test. The Friedman test will be used to compare ordinal outcome measures. Agreement between home sleep testing and in-laboratory PSGs will also be compared using Bland-Altman Analysis ¹⁴. A General Linear Model Approach will be used to explore the role of potential confounders including age, sex, weight, and race differences when performing analyses. If our hypothesis is correct, home sleep studies will be feasible in our study population.

7. Potential Risks

7.1. Unattended Polysomnography: There is minimal risk associated with the sleep study. Per AASM guidelines ³ unattended portable monitoring may be used to facilitate the diagnosis of OSA in adults and as such this is standard of care in that population. While no such recommendation for the use of unattended portable monitoring exists for pediatric patients, we will use an FDA approved device to perform the unattended polysomnography and patients and their families will be instructed in its use by a trained member of the research team. Patients and their families will also be provided a pictorial instruction manual on the proper application and use of the device. Family members will be instructed that the improper use of the device may present a choking hazard to their child. Family members will be instructed to listen out for their child throughout the night (for example by keeping bedroom doors open), and to check on their child for proper nasal cannula, effort belt, and pulse ox placement at least every two hours.

Patients may experience mild discomfort from the ambulatory sleep monitoring devices. Patients' family members may experience mild inconvenience during the setup of the sleep monitor, while monitoring of their child during the home sleep study, and should any trouble shooting be required during the time their child is asleep. Patients and their families may experience mild inconvenience if they are asked to perform a second sleep study due to results from the first study being uninterpretable.

7.2. In-laboratory Polysomnography: This is standard of care in the diagnosis of pediatric sleep disordered breathing. The in-laboratory polysomnogram is being conducted in an AASM accredited sleep disorder center that conducts 1300 sleep studies per year and has been in continuous operation since 1993. There is minimal risk associated with in-patient polysomnography. Patients may experience mild anxiety and discomfort by sleeping in an unfamiliar place for one night.

7.3 Steps Taken to Mitigate Risk: Studies are conducted under the supervision of the investigating physicians and personnel with specialty training in sleep medicine. Research team members are trained and experienced in performing research in human subjects, and in monitoring for adverse effects.

CONFIDENTIAL: This document is the intellectual property of [name], [name], and [name], PhD. Acceptance of this document constitutes the agreement by the recipient that no unpublished information contained herein will be published or disclosed without prior written approval.

Inclusion and exclusion criteria, monitoring, and the clinical protocol are designed to ensure that risks are absolutely minimal. Subjects and their families are informed that participation is voluntary and they may refuse to participate and may withdraw from the study at any time without penalty. Subjects will be told that in the unlikely event of a physical injury as the direct result of study procedures, they will be cared for by a member of the investigating team at no cost, within the limits of the Washington University compensation plan.

During the unattended sleep study, there is minimal risk. Subjects will be in their own home and should the unattended sleep study equipment prove too much of a discomfort or too challenging for parents to maintain they will be free to remove the device at any time. A specific monitoring plan to minimize the possibility that the device could present a choking hazard is described above. In-laboratory, attended polysomnography is standard of care and as such carries minimal risk.

Regarding confidentiality; 1) all subjects will be assigned a study ID number, and 2) unattended polysomnography reports will be kept confidentially. They will be coded, with information linking code numbers to names kept at a separate location, under lock and key. 3) The link to identifiers will be destroyed at the end of the study. 4) Data will be stored under lock and key (office, file cabinet) and only the investigators and research team will have access. If data are published, there will be no link to identifiers. Study data will not be revealed to any organization, individuals other than the subjects, or the subjects themselves. 5) Study data from the unattended polysomnography will not be entered in subjects' medical records.

8. Management of Intercurrent Events

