The purpose of the study proposed below is twofold. First we will test the feasibility of conducting portable sleep monitoring in school aged children using the Clevemed Sleepview (www.clevemed.com), one of the smallest portable sleep monitors commercially available at 57 grams. Second we will perform a direct comparison between the results obtained with this portable sleep monitor and those obtained from a standard-of-care in-laboratory attended sleep study performed at the St. Louis Children's Hospital Pediatric Sleep Center. These comparisons will be offered to the families of school age children suspected of having sleep disordered breathing who present to the Washington University Pediatric Otolaryngology Department. We hypothesize that in-laboratory attended polysomnography and portable monitoring will yield similar results in the diagnosis of sleep disordered breathing in school aged pediatric patients. These initial comparisons will be conducted in otherwise healthy children. Future studies will expand this comparison to children with underlying comorbidities, including younger children and those with developmental delay.

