4.1. Study design: Single-center, un-blinded, feasibility, and methods comparison study

4.2. Otolaryngology Clinic Assessment: Subjects will be identified from patients presenting to the Washington University in St. Louis Pediatric Otolaryngology Clinic who are suspected of having sleep disordered breathing. Subjects who are identified by an attending otolaryngologist as requiring polysomnography as part of their work up will then be approached by a member of the research team who will explain the study to the subject and their family and obtain informed consent. During this visit, subjects will also be administered a short, validated sleep questionnaire, the Modified STOP-Bang Tool for Stratifying OSA Risk in Adolescent Children ⁹. This questionnaire is 8 questions and routinely administered in the Washington University Pediatric Otolaryngology offices.

4.3.1. Unattended Polysomnography: All eligible subjects will be asked to conduct an unattended, overnight sleep study performed in their home prior to in-laboratory polysomnography, using a standard Type III portable monitor. This study will be performed with

an FDA approved sleep monitor (e.g CleveMed SleepView or similar). Per American Academy of Sleep Medicine (AASM) guidelines, portable sleep monitoring will include air flow, respiratory effort, heart rate and blood oxygenation. Airflow will be measured using a nasal cannula and pressure transducer which is located within the home sleep test (HST) recording device. Respiratory effort will be recorded using Respiratory Inductance Plethysmography (RIP) belts that will go around the chest at the nipple line and around the abdomen at the navel level. Blood oxygenation and heart rate will be recorded by pulse oximetry that will be placed on one finger. Each study participant and their family will be shown and educated on how to apply each of the sensors by a member of the study team. Unattended sleep studies will be interpreted by an individual trained in sleep medicine. The first assessment of the Unattended sleep study for each individual patient will be readability of the recordings.

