Polysomnography testing will determine the apnea hypopnea index (AHI), blood saturation oxygen nadir (SPO₂ nadir), and average blood oxygen saturation ³. The AHI is defined as the average number of hypopneas (episodes of decreased breathing) and apneas (episodes of cessation of breathing) per hour of sleep. Apneas and hypopneas will be defined per the American Academy of Sleep Medicine manual for scoring sleep and associated events ¹⁰. The objective is to obtain greater than or equal to 6 hours of data adequate for polysomnography analysis and determination of an apnea hypopnea index (AHI), average SPO₂, and SPO₂ nadir using home un-attended polysomnography.

A McGill Oximetry Score ¹¹, which only uses the frequency and depth of SPO₂ desaturations throughout a night's sleep to assign a score of 1 (normal/inconclusive), 2 (mildly abnormal), 3 (markedly abnormal), and 4 (severely abnormal) will be also be assigned to each home sleep test.

Fidelity of data collection using at home sleep studies is reliable, but not 100% reliable ³. For example, subjects may unconsciously remove the nasal cannula or the finger pulse oximeter in their sleep, resulting in data drop outs. A subject's parent or guardian will be requested to periodically monitor the subject throughout the night and be instructed on how to reapply sensors to minimize data drop outs. Should data from an initial sleep study be uninterpretable based on sleep study expert opinion we will ask the subjects to attempt the unattended sleep study an additional time. A recent study on the feasibility of Type II comprehensive (i.e. greater than 7 channel) pediatric sleep studies, reported that 91% of home sleep studies are successful on initial attempt and a total of 98% are successful after one repeat testing ¹². A 2013 assessment of Type III sleep studies performed both in a hospital setting (26 patients) and at home (75 patients) found that technically acceptable and interpretable studies were obtained from 93% of subjects ¹³.

Should data from the second sleep study be uninterpretable we will not proceed with further testing of these subjects by home sleep study. Regardless of whether a subject successful completes home sleep testing, in-laboratory polysomnography will still be performed as part of their work up for sleep disordered breathing.

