Per American Academy of Sleep Medicine (AASM) guidelines, in-laboratory sleep monitoring is attended by a specially trained technologist who sets up the sleep study, observes the subject throughout the duration of the sleep study, and is available to troubleshoot in real time any monitoring issues that may arise. In-laboratory polysomnography consists of 21 leads that measure electroencephalogram, electrocardiogram, air flow, respiratory effort, heart rate, activity, and blood oxygenation monitoring. In-laboratory sleep studies are scored by a trained Registered Polysomnographic Technologist or Registered Sleep Technologist and interpreted by a physician. Polysomnography testing will determine the sleep stages, apnea hypopnea index (AHI), blood saturation oxygen nadir (SPO₂ nadir), and average blood oxygen saturation, as defined above ³. A McGill Oximetry Score will also be calculated for the in-laboratory PSG.

4.6. Subject assessments: The unattended home polysomnogram will record blood oxygen concentration, pulse rate, respiratory effort, air flow and respiratory effort. The in-laboratory polysomnogram will record these parameters and will also measure electroencephalography, electrocardiogram, and heart rate.

4.7. Conclusion of study: The study ends with the completion of the in-laboratory polysomnogram. Additionally, the study ends at any time the patient or parent/caregiver requests it to end. Appropriate treatment for any diagnosis of sleep disordered breathing will proceed based on the attending otolaryngologist recommendations. Recommendations and treatment will not be affected by participation in the investigation. As home sleep testing in pediatric patients is exploratory; only the in-laboratory sleep study will be used in making any diagnosis of sleep disordered breathing and in determining treatment options.

5. Data Collection and Monitoring

5.1. Clinical Assessments: At the completion of both the unattended and in-laboratory polysomnography we will determine an Apnea-Hypopnea Index, Average SPO₂, and SPO₂ nadir for each subject. An assessment of the technical quality of each study will be made. The in-laboratory polysomnogram will be scored and interpreted via standard practice for the St. Louis Children's Hospital Pediatric Sleep Center and included in the patient's medical record. The unattended polysomnogram will not be included in the patient's medical record and will only be accessible to study team members.

6. Outcome Measures

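### Section 6.4 fixes a Friedman test for the ordinal McGill score; with two paired methods that is a sign test of directional shift and cannot show whether home and laboratory scores agree

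*Protocol*

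**What the plan says.** The Protocol's Section 6.4 names one method for ordinal outcomes: "The Friedman test will be used to compare ordinal outcome measures".

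The McGill score is the only outcome that the Protocol defines as ordinal. Section 4.3.1 describes it as a score read from the oximetry trace of each home study: "assign a score of 1 (normal/inconclusive), 2 (mildly abnormal), 3 (markedly abnormal), and 4 (severely abnormal". Section 4.4 adds the second measurement: "A McGill Oximetry Score will also be calculated for the in-laboratory PSG". Section 6.3 makes the pair an exploratory outcome: "Comparison of McGill Oximetry Scores between unattended and in-laboratory polysomnography". So there are exactly two measurements per child.

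Section 4.1 gives the design as "Single-center, un-blinded, feasibility, and methods comparison study". The hypothesis in Section 1, stated for the diagnosis of sleep disordered breathing, is that "in-laboratory attended polysomnography and portable monitoring will yield similar results". The one agreement method in Section 6.4 comes straight after the Friedman sentence and names no outcome: "Agreement between home sleep testing and in-laboratory PSGs will also be compared using Bland-Altman Analysis".

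**The concern.** The Friedman test is meant for three or more related conditions. With two, it keeps only the direction of each disagreement. A non-significant result then means that upward and downward disagreements roughly balance, which can happen when agreement is excellent, poor or no better than chance. A significant result means that disagreements lean one way, which can happen when nearly all pairs agree.

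The study sets out to learn whether a home device gives results like the laboratory's. If the McGill comparison is reported by this p-value, a large value may be read as agreement and a small one as disagreement, and neither reading is justified.

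**Working it through.** **Inputs.** Two paired methods (Sections 4.3.1, 4.4 and 6.3); four grades (Section 4.3.1); 100 pairs, the planned number of study patients in Section 2. That section's enrolment figure reproduces: 100 / (1 − 0.20) = 125. The Protocol gives no McGill data, so the tables below are assumed. The identity in step 1 needs no data.

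**Step 1: Friedman with two conditions.** Let *n* be the number of pairs, *u* the pairs where home is higher and *d* the pairs where home is lower. Within a pair the ranks are (1, 2), (2, 1) or, for a tie, (1.5, 1.5). The rank sums are therefore 1.5*n* ± (*u* − *d*)/2.

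- Uncorrected statistic with k = 2: (2/*n*) × [4.5*n*² + (*u* − *d*)²/2] − 9*n* = (*u* − *d*)²/*n*.
- Tie correction: 1 − 6(*n* − *u* − *d*)/(6*n*) = (*u* + *d*)/*n*.
- Corrected statistic: **Q = (*u* − *d*)²/(*u* + *d*)**, which is the sign-test chi-square on 1 degree of freedom.

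A numerical check on 5000 random data sets of 100 pairs of four-level scores found the two statistics equal to within 1e-13. Agreeing pairs drop out, and a three-grade disagreement counts the same as a one-grade one.

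**Step 2: three assumed tables.** Rows are laboratory grades 1 to 4; columns are home grades 1 to 4.

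- A: [56,3,0,0], [3,19,1,0], [0,1,9,1], [0,0,1,6]
- B: [40,8,4,2], [8,10,3,1], [4,3,6,2], [2,1,2,4]
- C: [50,6,0,0], [1,21,3,0], [0,0,10,2], [0,0,0,7]

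Linear weighted kappa = 1 − (observed sum of absolute grade differences) / (sum expected from the margins):

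- A: 1 − 10/90.92 = 0.890
- B: 1 − 58/102.54 = 0.434
- C: 1 − 12/97.26 = 0.877

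| | A | B | C |
|---|---|---|---|
| Exact agreement (exact 95% CI) | 90% (82–95) | 60% (50–70) | 88% (80–94) |
| Home higher / lower | 5 / 5 | 20 / 20 | 11 / 1 |
| Pairs two or more grades apart | 0 | 14 | 0 |
| Q | 0²/10 = 0 | 0²/40 = 0 | 10²/12 = 8.33 |
| Friedman p | 1.00 | 1.00 | 0.004 |
| Exact sign test p | 1.00 | 1.00 | 0.006 |
| Wilcoxon signed rank p (normal approximation, zeros dropped) | 1.00 | 1.00 | 0.004 |
| Linear weighted kappa (95% CI) | 0.89 (0.82–0.96) | 0.43 (0.28–0.59) | 0.88 (0.81–0.94) |
| Quadratic weighted kappa | 0.94 | 0.49 | 0.93 |

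The planned test cannot tell A from B, yet flags C, whose agreement is close to A's.

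**Step 3: more extreme assumed tables, also 100 pairs.** With every pair discordant but balanced (25 each of 1/4, 4/1, 2/3 and 3/2), agreement is 0% and Friedman p = 1.00. With 92 agreeing pairs and 8 one-grade shifts all one way, Q = 8²/8 = 8.0 and p = 0.005.

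**Step 4: Bland-Altman on the same scores.** The limits are mean ± 1.96 SD of home minus laboratory.

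- A: 0 ± 1.96 × 0.318 = −0.62 to 0.62 grades; 10 of 100 pairs fall outside.
- B: 0 ± 1.96 × 1.015 = −1.99 to 1.99; 14 outside.
- C: 0.10 ± 1.96 × 0.333 = −0.55 to 0.75; 12 outside.

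The limits rank B worst, correctly. But differences come only in whole grades, so limits meant to leave out about 5 pairs leave out 10 to 14. In A and C every disagreeing pair lies outside them.

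**The case against.** The case on the other side has five parts.

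- **Friedman is a valid shift test, and the remedy keeps one.** True: a sign test with two methods is the Friedman test. What changes is that agreement becomes the reported result and the shift test a side check.
- **Kappa and a cross-table could sit in an analysis plan that is not shown.** They could. But the Protocol is not silent here: it names a method for ordinal outcomes, and that method does not measure agreement.
- **Section 6.4 handles agreement separately, by Bland-Altman, and does not confine it to continuous outcomes.** This is the strongest point. If the sentence covers McGill, the plan does separate good from poor agreement, though crudely, as step 4 shows. The text does not settle whether it does.
- **The Protocol claims no agreement for McGill.** Section 6.3 speaks only of comparison, the similarity hypothesis concerns diagnosis, and no rule equates non-significance with agreement. That stands, and it means the harm lies in how the p-value is read.
- **The tables are chosen.** A and B are symmetric, so p = 1.00 follows by construction. The identical Wilcoxon p-values arise because A and C contain only one-grade differences and B is symmetric. In other tables the two tests part. Ten one-grade shifts one way against ten three-grade shifts the other give Friedman 1.00 and Wilcoxon 0.055. Fourteen one-grade rises against six two-grade falls give Q = 8²/20 = 3.2 (p = 0.07) and Wilcoxon 1.00. So Wilcoxon does use magnitude. It is still a test of shift, and no shift test measures agreement.

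**Conclusion.** The concern holds, at minor severity. The equivalence of Friedman and the sign test is exact for any two-method data. The percentages, kappas and p-values rest on assumed tables and show what can happen, not what this trial will find.

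The effect is confined to the exploratory outcome in Section 6.3. The primary feasibility outcome and the AHI and SpO₂ comparisons do not use this test. The diagnosis comparison in Section 6.2.4 would come under the same sentence only if diagnosis were graded on an ordered scale, which the Protocol does not say.

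**What to change.** Replace the Friedman sentence in Section 6.4 with one along these lines:

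> McGill scores will be compared by the 4×4 home-by-laboratory table, percent exact agreement and linearly weighted kappa, each estimate with a 95% confidence interval; a sign or Wilcoxon signed rank test will be used only to check for directional shift.

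State the weights in advance, because linear and quadratic weights give different values on the same table (A 0.89 against 0.94; B 0.43 against 0.49; C 0.88 against 0.93). Say also which outcomes the Bland-Altman sentence covers.

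The cost is one or two sentences, with no new data and no change to sample size. The drawback is that kappa depends on how common each grade is, so the full table must be shown beside it.

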8.1. Adverse Experiences

The investigator will closely monitor subjects for evidence of adverse events. All adverse events will be reported and followed until satisfactory resolution. The description of the adverse experience will include the time of onset, duration, intensity, etiology, relationship to the study drug (none, unlikely, possible, probable, highly probable), and any treatment required.

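### Sections 5.1 and 7.3 bar disclosure of home-test results outside the study team without exception, so physician investigators have no stated permission to tell the family or the treating otolaryngologist about a severe recording

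*Protocol*

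**What the plan says.** Section 4.3.1 places the home test first, as an "overnight sleep study performed in their home prior to in-laboratory polysomnography". On reading it says: "Unattended sleep studies will be interpreted by an individual trained in sleep medicine". The McGill scale runs from 1 to 4, and grades "3 (markedly abnormal), and 4 (severely abnormal) will be also be assigned to each home sleep test".

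On disclosure, section 5.1 says: "The unattended polysomnogram will not be included in the patient's medical record", and limits access to the study team. The confidentiality list in section 7.3 repeats the bar on the record, gives access to investigators and research team only, has the identifier link destroyed when the study ends, and adds: "Study data will not be revealed to any organization, individuals other than the subjects, or the subjects themselves". Section 4.7 calls home testing in children exploratory and lets only the laboratory study inform diagnosis and treatment, which follow the attending otolaryngologist's recommendations.

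On safety, section 7.3 has investigating physicians supervise the studies. Section 8.1 covers adverse events in general terms. Section 9 gives the investigating physicians a monitoring role and binds them to the IRB's reporting requirements.

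**The concern.** The children are enrolled because sleep disordered breathing is suspected, so some abnormal home recordings are foreseeable. The study produces a graded oximetry result for each child, together with an AHI, an average saturation and a nadir, and then applies a non-disclosure rule with no exception. A team member who follows that rule literally may not tell a parent or the treating clinician about a severe recording.

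For most children the laboratory study would be expected to bring the same problem to light. A child who leaves before that night may have no such second look within the study, and once the identifier link is destroyed the home result can no longer be traced to the child. The issue is an absolute rule that the protocol itself fixes. It is not a detail that a statistical analysis plan would supply.

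**Working it through.** The protocol gives no figure to reproduce, so the check sets its statements side by side.

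1. **Is a severe finding known to the team?** Yes, once the recording is scored. A trained reader interprets it (4.3.1), a McGill grade is assigned to each home test (4.3.1), and AHI, average saturation and nadir are derived (5.1).

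2. **When is it known?** Not stated. The repeat rule in 4.3.1, "Should data from an initial sleep study be uninterpretable based on sleep study expert opinion", means that an expert looks at the first recording while the child is still taking part, but only interpretability has to be judged then. Section 5.1 has the AHI and saturation values determined once both studies are complete. That can mean after both nights, or after each in turn. No time is given for the McGill grade, and no maximum interval between the two tests.

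3. **Who may be told?** Section 5.1: the study team. Section 7.3: no organization, no other individual, not the subject. Together these exclude the parents, the child and any clinician outside the team.

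4. **May the result be used in care?** Section 4.7: no.

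5. **Is there an exception anywhere?** The parental plan (4.3.2) and the risk text (7.1) cover sensor checks and choking, not what the recording shows. Section 8.1 does not class a severe recording as an adverse event. Section 8.2 lets the investigator withdraw a subject in the subject's interest but says nothing about disclosure. Section 9 refers to adverse events and IRB policy in general. None of them qualifies 5.1 or 7.3.

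6. **Literal reach of the 7.3 sentence.** It speaks of study data without qualification. Read literally, it also covers the laboratory result, which 5.1 puts in the medical record, and it bars disclosure to the IRB as an organization, although section 9 requires reporting under IRB policy. The sentence needs a narrower scope to be workable.

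7. **Who is exposed?**
   - *Children without a laboratory night.* Section 2 plans 125 enrolled with 20% drop-out: 125 × 0.20 = 25, leaving 100. How many of the 25 would have a home recording but no laboratory study is not stated, so the count lies between 0 and 25.
   - *Illustration only.* Assume that 1% to 5% of recordings reach the top grade; the documents give no rate. If all 25 had a recording and no laboratory night, the expected number is 25 × 0.01 = 0.25 to 25 × 0.05 = 1.25 children. Among the 100 who complete both tests it is 100 × 0.01 = 1 to 100 × 0.05 = 5, and these count only if the recording was read before the laboratory night.

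**The case against.** The strongest reply is that withholding is deliberate and defensible. Home testing in children is called exploratory, the device is not approved for children (4.3.2), and every eligible child is to have a laboratory study that enters the record whatever the home test shows. That study is routine care, so a child who leaves the research may still have it. All of this stands, and it limits the weight of the point. It does not supply an exception for a child whose laboratory night is delayed or never happens.

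Several stronger readings are tempting, and the documents do not support them:

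- **A severe finding reaches no one responsible for the child.** Investigating physicians supervise the studies, have access to the data and take part in monitoring, and the team includes otolaryngology faculty and the sleep laboratory's director. What is missing is permission to go beyond the team.
- **The grade is known before the laboratory night.** This is an inference from the repeat rule. Section 5.1 may place derivation of the home values after both nights.
- **The bar contradicts the adverse event section.** Section 8.1 says "The investigator will closely monitor subjects for evidence of adverse events", but nothing classes desaturation from the suspected condition as an adverse event, so no conflict is shown.
- **Section 7.3 is meant to hide the laboratory result.** The neighbouring items in the list concern the home recordings, so in context the sentence mainly means those. The clash with 5.1 is one of literal wording.

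The consent pages are not in the file, and the IRB policies are only cited. Either may deal with incidental findings. If so, the absolute wording of 5.1 and 7.3 would still have to be reconciled with them.

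**Conclusion.** The point holds in a limited form. Sections 5.1 and 7.3 bar home results from the record and from everyone outside the team, without exception, while the same team grades each recording up to severely abnormal. Physician investigators can see the result but have no stated permission to tell the family or the treating otolaryngologist. The 7.3 sentence is also wider than 5.1 and section 9 allow.

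The size cannot be derived from the documents. The most exposed group is whatever part of the 25 planned drop-outs has a home recording and no laboratory study. For the others, exposure depends on when recordings are read and how long the wait is, and neither is stated. The 1% to 5% rate is an assumption and carries no weight in the conclusion. The change should be made because a child's safety could depend on it and the cost is low. The primary feasibility result is not affected, since it depends only on hours of analysable home data.

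**What to change.** - Limit the non-disclosure sentence in 7.3 to home-test data.
- Replace its absolute form with one that allows a written safety exception, under which the physician investigators may disclose a home result beyond the study team. Routing results only to those physicians would change nothing, because they already have access.
- Reconcile 4.7, 5.1, 7.3 and section 9 with that exception, and match the consent wording. State when home recordings are scored, since this decides whether the exception can apply before the laboratory night.
- Flag each child whose home result was disclosed before the laboratory study, and repeat the home-versus-laboratory comparison without these children. Report it beside the full analysis, not in its place, because removing severe cases narrows the range over which agreement is judged.

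The trigger for disclosure and the clinical response are for the clinicians and the IRB to set; none is proposed here.

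The cost is about one paragraph of protocol text, matching consent wording and one data field. The downside is small: a few laboratory readings may no longer be independent of the home result, and the flag identifies them.
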